### ***Pregnancy***

Since HMG-CoA reductase inhibitors decrease cholesterol synthesis and possibly synthesis of other biologically active substances derived from cholesterol, they are contraindicated during pregnancy and in nursing mothers.

The Investigator will immediately notify the Sponsor of any pregnancy that is discovered during study drug administration or which started during study drug administration. Pregnancy forms will be completed for all pregnancies reported during the clinical trial. In addition, with the permission of the study participant, or female partner of a male participant, the investigator will report follow-up information regarding the outcome of the s, including perinatal and neonatal outcome. Infants will be followed for 6 months.

All women of childbearing potential will be instructed to contact the study team immediately if they suspect they might have become pregnant (for example, missed or late menses) during study treatment or within one month of receiving their last dose of study medication.

If pregnancy is suspected for a participant in the experimental arm while the participant is receiving pravastatin, the pravastatin will be withheld immediately until the result of the pregnancy test is known. If pregnancy is confirmed, the pravastatin will be permanently discontinued in an appropriate manner and the participant withdrawn from the trial. Protocol-required procedures for trial discontinuation and follow-up will be performed unless contraindicated by the pregnancy. Patients will be referred to prenatal care and to the local TB program for continuation of their TB treatment. Women will be asked questions about pregnancy history as well as information about the current pregnancy and birth. Permission will also be requested to follow the infant for six months.

Should the female partner of a male participant enrolled in the pravastatin arm become pregnant during the study or in the 4 weeks after the completion of pravastatin (Week 16 after study entry) and the Investigator becomes aware that this situation has occurred, consent will be requested from the female partner for collection of information on her pregnancy history and for information on the current pregnancy and birth. Permission will also be requested to follow the infant for six months.

Pregnancy reporting will follow the same time lines and reporting structures as for a SAE (see above), but by using Pregnancy forms to be sent to the data management center. SAE reporting will also occur if the pregnancy outcome is a congenital anomaly. This will follow the reporting procedures described above for SAE reporting plus an additional clinical report.

### ***Clinical Management of Adverse Events***

#### Liver toxicity

Study treatment will be permanently discontinued if any of the following criteria are met:

- ALT > 5x the upper limit of normal (ULN) without symptoms
- ALT > 3x ULN with signs or symptoms suggestive of clinical hepatitis including one or more of the following: nausea, vomiting, abdominal pain, dark colored urine or clay colored stools, unexplained fever, jaundice, liver tenderness, or hepatomegaly
- ALT > 3x ULN and Total Bilirubin  $\geq$  2x ULN

If a patient develops hepatic toxicity meeting the above stopping criteria, the following evaluation will be undertaken: assessment for history of injection or non-injection drug use, alcohol ingestion, use of other hepatotoxic drugs, and performance of serologic tests for viral hepatitis (IgM antibody for Hepatitis A, Hepatitis B surface antigen, IgM antibody to Hepatitis B core antigen, antibody to Hepatitis C). In addition, an AST and INR should also be checked, if not already done.

Participants will be followed until resolution (return to baseline) or stabilization of the ALT elevation.

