### ***Severity\****

With the exception of creatinine kinase elevation, all symptoms and laboratory findings will be graded according to severity using the Division of AIDS Table for Grading Severity of Adult and Pediatric Adverse Events, Corrected Version 2.1, July 2017, which, in our view is the most comprehensive grading scale for patients with infectious diseases, including TB or HIV.

The protocol-specific criteria for grading elevated CK are as follows:

PARAMETER	GRADE 1 MILD	GRADE 2 MODERATE	GRADE 3 SEVERE	GRADE 4 POTENTIALLY LIFE-THREATENING
Creatinine kinase, high	3 to < 6 x ULN	6 to < 10 x ULN	10 to < 20 x ULN	> 20 x ULN

The DAIDS toxicity table criteria for grading liver function tests are as follows:

PARAMETER	GRADE 1 MILD	GRADE 2 MODERATE	GRADE 3 SEVERE	GRADE 4 POTENTIALLY LIFE-THREATENING
AST or SGOT, High	1.25 to < 2.5 x ULN	2.5 to < 5.0 x ULN	5.0 to < 10.0 x ULN	≥ 10.0 x ULN
ALT or SGPT, High	1.25 to < 2.5 x ULN	2.5 to < 5.0 x ULN	5.0 to < 10.0 x ULN	≥ 10.0 x ULN
Total bilirubin	1.1 to < 1.6 x ULN	1.6 to < 2.6 x ULN	2.6 to < 5.0 x ULN	≥ 5.0 x ULN

\*The DAIDS AE Grading Table is available at: <https://rsc.niaid.nih.gov/clinical-research-sites/daids-adverse-event-grading-tables>.

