#### Other toxicities

Grade 1 toxicities: In general, for grade 1 toxicities, the patient will be followed carefully, and the study drugs will be continued.

Grade 2 toxicities: For grade 2 toxicities, the patient will be followed more carefully, with additional laboratory and/or clinic visits as necessary, and the study drugs temporarily held at the investigator's discretion.

Grade 3 toxicities: For any grade 3 toxicity involving creatinine kinase elevation, with or without myopathy, myalgias, hepatitis, nausea/vomiting, and/or diarrhea, that, in the principal investigator's judgment is due to study drug, the study drug will be discontinued. The clinician should rule out other possible causes of the symptoms before discontinuing study medication. When possible, concomitant medications should be held first at the discretion of the principal investigator if he/she suspects they are contributing to the toxicity. In the event of study product discontinuation, management of the standard of care TB drugs will revert to the site clinician as per local practice.

Grade 4 toxicities: Any patient with grade 4 renal, hepatic, cardiac or hematological toxicity will be immediately discontinued from study therapy. The laboratory test or clinical finding in question will be reassessed as soon as possible. The repeat test will guide management of the event as follows:

- If the repeat assessment shows toxicity of grade 3 or lower, and if the patient has continued to receive study drugs between the two testing dates, then the patient will be managed according to the appropriate toxicity level of the repeat test.
- If the repeat test shows toxicity of grade 3 or lower, and if the participant has not received study drugs between the two testing dates, then the participant will be managed at the discretion of the investigator with regard to the re-administration of study drugs, and otherwise according to the toxicity level of the repeat test.
- If the repeat test shows grade 4 toxicity, then the participant will be permanently discontinued from study medications. Further treatment of TB will be directed by the investigator on an individualized basis. The participant will continue to be followed for study monitoring purposes (as are other participants who make a permanent departure).

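### For ALT at or above 10 times ULN, the Liver toxicity rule requires a permanent stop while the grade 4 rule under Other toxicities can leave re-administration to the investigator, and no precedence is stated

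*Combined protocol and SAP*

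**What the plan says.** Two subsections of Section 5, Clinical Management of Adverse Events, apply to liver events.

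- **Liver toxicity.** "Study treatment will be permanently discontinued if any of the following criteria are met". Three triggers are then listed, of which the first is "ALT > 5x the upper limit of normal (ULN) without symptoms". The second lowers the ALT limit to 3 times ULN when there are clinical features of hepatitis, and the third combines ALT above 3 times ULN with total bilirubin of at least 2 times ULN. The work-up that follows is diagnostic. It contains no step by which treatment could resume.
- **Other toxicities, grade 4.** "Any patient with grade 4 renal, hepatic, cardiac or hematological toxicity will be immediately discontinued from study therapy". The finding is then reassessed: "The repeat test will guide management of the event as follows". If the repeat is grade 3 or lower and no drug was taken in between, the participant is "managed at the discretion of the investigator with regard to the re-administration of study drugs"; the grade of the repeat decides the rest. If the repeat is still grade 4, the stop is permanent. The next paragraph makes the stop permanent for all other grade 4 toxicities.
- **Other toxicities, grade 3.** For a list of events that includes hepatitis, the drug is stopped if the principal investigator judges the event to be due to study drug.

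The Severity table grades ALT of "5.0 to < 10.0 x ULN" as grade 3 and ALT of 10 times ULN or more as grade 4. Section 9 makes liver toxicity a mandatory reason to stop and points back to the Clinical Management section for the details.

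**The concern.** A grade 4 ALT result satisfies the Liver toxicity criteria and also falls under the grade 4 paragraph, and the two prescribe different management. Two investigators could each follow the protocol and treat the same participant in opposite ways, one stopping pravastatin for good and the other considering a restart.

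Three things are at stake. The first is participant safety. The second is the secondary endpoint in Safety and Tolerability Endpoints, which counts permanent discontinuation of the regimen for almost any reason, whatever the attribution. The third is who is replaced and who contributes Day 15 PK: under Section 9, participants who stop early are replaced and their later visits carry no PK sampling.

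**Working it through.** No power or sample-size arithmetic applies. The check puts the thresholds on one scale and applies both rules to the same values.

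**Step 1: overlap.** An ALT of 10 times ULN or more exceeds 5 (the limit without symptoms) and exceeds 3 (the limit with symptoms). Every grade 4 ALT event therefore meets a Liver toxicity criterion, with or without symptoms.

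**Step 2: the rules side by side.** The ALT values are illustrative. The participant has no symptoms, bilirubin is below 2 times ULN, and the drug is held after the first result.

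| First ALT (x ULN) | Repeat ALT (x ULN) | Liver toxicity rule | Grade 4 paragraph |
|---|---|---|---|
| 12 (grade 4) | 12 (grade 4) | Permanent stop | Permanent stop |
| 12 (grade 4) | 8 (grade 3) | Permanent stop; 8 > 5 would also suffice alone | Re-administration at discretion, otherwise by repeat grade |
| 12 (grade 4) | 4 (grade 2) | Permanent stop, from the first value | Re-administration at discretion, otherwise by repeat grade |

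The last row is the cleanest conflict. A repeat of 4 times ULN in this participant meets no Liver toxicity criterion, so managing by the repeat grade does not lead back to a permanent stop. Only the first value requires one, and the grade 4 paragraph lets the repeat supersede it.

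**Step 3: grade 3.** The Liver toxicity rule is unconditional once a criterion is met. The grade 3 paragraph makes the stop for hepatitis depend on attribution to study drug. An ALT of 6 times ULN with jaundice, judged not due to study drug, is a permanent stop under the first rule and is not required to stop under the second.

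**Step 4: boundary.** The Liver toxicity criteria all require raised ALT. Grade 4 AST, or grade 4 bilirubin (5 times ULN or more), with ALT at or below 3 times ULN meets none of them, so only the grade 4 paragraph applies and there is no conflict.

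**Step 5: timing.** Scheduled liver tests after screening fall on Days 7, 15, 21 and 30, and dosing ends on Day 15. A restart is therefore a live question mainly after the Day 7 test or an unscheduled test.

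**Step 6: reach into the data.** In an arm of 5 or 10 treated participants, one participant moves the permanent-discontinuation proportion by 1/5 = 20 or 1/10 = 10 percentage points. If the replacement is added to the denominator, these become 1/6 = 17 and 1/11 = 9. The PK effect is less certain. A permanent stop after Day 7 removes the Day 15 profile. A restarted participant might keep it, but Section 9 also treats more than two missed doses as non-compliance and does not say whether doses held for safety count.

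**The case against.** The strongest reply is that the Liver toxicity rule governs and the grade 4 paragraph only fills gaps. It is the dedicated rule and has no upper limit. The other text sits under the heading Other toxicities. The word hepatic there still has work to do for AST and bilirubin events. Section 9 names liver toxicity, CK elevation, and myalgias and myopathy, which match the three dedicated subsections in order.

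This may well be the intent, and the AST and bilirubin argument stands as a limit on the point. It does not settle the text. The heading is not exclusive, because its grade 3 paragraph covers CK elevation, myalgias and hepatitis, all of which have or overlap with dedicated rules. The grade 4 paragraph does not restrict hepatic to AST or bilirubin. By making other grade 4 events permanent, the paragraph after it keeps hepatic events on the re-test route. Section 9 refers to the whole Clinical Management section, which holds both rules.

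Three stronger readings are tempting, and the documents do not support them:

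- *The more severe event gets the more lenient rule.* This follows only if the grade 4 paragraph displaces the Liver toxicity rule. As written, that rule also covers 12 times ULN, and the grade 4 paragraph requires an immediate stop first and only then allows discretion.
- *The grade 4 paragraph contradicts itself by providing for the case* "if the patient has continued to receive study drugs between the two testing dates". With daily dosing, a participant can take doses after the first sample and before its result is known. The clause plausibly covers that.
- *One such participant decides the arm.* Data Analysis counts any treatment discontinuation for a pravastatin-related reaction, and the grade 4 paragraph also discontinues treatment, so that criterion can be met under either rule. The two decision-making algorithms count events, and a grade 4 ALT counts the same there however it is managed. The isoniazid and pyrazinamide hepatotoxicity described in Section 13 does not help this reading, because events due to those drugs alone are not pravastatin-related.

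**Conclusion.** The point holds as a conflict between two stated safety rules for the same ALT event. It covers every grade 4 ALT event whose repeat is grade 3 or lower with the drug held. The attribution condition for grade 3 hepatitis is a related mismatch. The effects are on participant safety, on the permanent-discontinuation secondary endpoint, and possibly on replacement and PK evaluability. No effect on dose escalation is shown.

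The size in practice cannot be computed. The documents give no rate of grade 4 ALT; their figures of 10-20% aminotransferase elevation on isoniazid and 1.3% hepatotoxicity on pyrazinamide are not grade-specific. Entry criteria exclude ALT above 2.5 times ULN and positive hepatitis B or C tests, so few events are likely, but the arms have only 5 or 10 participants. The conclusion rests on reading hepatic in the grade 4 paragraph to include ALT, which the Severity table's liver function tests support and nothing in the text excludes.

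**What to change.** The sponsor and investigators should reconcile Liver toxicity, the grade 3 and grade 4 paragraphs of Other toxicities, and the liver item in Section 9 into one cross-referenced hepatic rule. The text should state which rule governs ALT-based grade 3 and grade 4 events, and whether the attribution condition applies to them. Section 9 should then point to that rule and not to the section as a whole. Which clinical rule is right is for the sponsor and investigators, and no view is given here.

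The cost is wording in a protocol amendment. Sample size, visits and the statistical methods do not change.

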#### Creatinine Kinase Elevation

For Grade 1 (3 to  $< 6 \times$  ULN) or Grade 2 (6 to  $< 10 \times$  ULN) creatinine kinase elevation, participants may continue study drug treatment and should be carefully evaluated and followed closely. For Grade 3 (10 to  $< 20 \times$  ULN) or higher creatinine kinase elevation, participants will permanently discontinue statin but will be requested to attend follow-up visits until study end.

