## 1. Abstract

Protocol Synopsis	
Protocol Title:	StAT- TB (Statin Adjunctive Therapy for TB): A Phase 2b Dose-finding Study of Pravastatin in Adults with Tuberculosis
Treatment Indication:	Pulmonary Tuberculosis (TB)
Trial Objective:	To assess the safety, tolerability, and pharmacokinetics of pravastatin adjunctive therapy when combined with the standard TB treatment regimen.
Trial Design:	Phase IIB clinical trial: A two-week safety/PK study to determine pravastatin exposures over 24 hours when given together with first-line treatment (HRZE) and ensure the combination is safe and well-tolerated.
Patient Population:	Up to 35 evaluable participants aged 18 years or older will be enrolled.
Treatment arms:	
5-10 participants per arm will be sequentially recruited to receive one of the following:
 
Arm 1: Pravastatin 40 mg and Rifafour (fixed-dose combination of isoniazid, rifampin, pyrazinamide, and ethambutol) daily for 14 days (pravastatin will be given alone on Day 1, and pravastatin + Rifafour will be given on Days 2-15) (5 participants if well tolerated)
 
Arm 2: Pravastatin 80 mg and Rifafour (fixed-dose combination of isoniazid, rifampin, pyrazinamide, and ethambutol) daily for 14 days (pravastatin will be given alone on Day 1, and pravastatin + Rifafour will be given on Days 2-15) (10 participants)
 
Arm 3 will only be recruited if pravastatin 80 mg is well tolerated and safe, yet drug exposures are significantly reduced due to the known interaction with rifampin.
 
Arm 3: Pravastatin 120 mg, and Rifafour (fixed-dose combination of isoniazid, rifampin, pyrazinamide, and ethambutol) daily for 14 days (pravastatin will be given alone on Day 1, and pravastatin +, Rifafour will be given on Days 2-15) (10 participants)
 
Arm 4 will only be recruited if pravastatin 120 mg is well tolerated and safe, yet drug exposures are significantly reduced due to the known interaction with rifampin.
 
Arm 4: Pravastatin 160 mg, and Rifafour (fixed-dose combination of isoniazid, rifampin, pyrazinamide, and ethambutol) daily for 14 days (pravastatin will be given alone on Day 1, and pravastatin + Rifafour will be given on Days 2-15) (10 participants)
 
Vitamin B6 will be added to each of the regimens.

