***Day 15 (Week 2)***

- Targeted symptom assessment
- Concomitant medications
- DOT
- Adverse event assessment
- Sputum
- Liver function tests
- Chemistry (Comprehensive metabolic panel:, total cholesterol, LDL, , C-reactive protein, uric acid)

- Urine pregnancy test
- Intensive PK for pravastatin
- Lung inflammation assessment (PFT, St. George's respiratory questionnaire, 6-minute walk test); +/- 3 days.
- CK, serum creatinine

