### ***Steady State Pharmacokinetic Assessments***

*Intensive PK sampling:* Each participant will have initial PK assessments for pravastatin at Day 1 (immediately prior to dose administration and at 0.5, 1, 1.5, 2, 3, 4, 6, and 8 hours post-dose) as well as single point PK assessment on Day 2 (trough level immediately before the 2nd dose and 4-6 hours after the 2nd dose of pravastatin). The post-dose PK assessment on Day 2 will be completed prior to the administration of the first dose of TB medications. Each participant will also have steady-state PK assessment at Day 15 immediately prior to administration of study medications and then at 0.5, 1, 1.5, 2, 3, 4, 6, and 8 hours post-dose. Samples will consist of 4cc of blood collected via an indwelling catheter or by direct venipuncture.

For participants who miss or vomit the first dose of pravastatin on Day 1, that visit should be rescheduled  $\geq 1$  day later and study procedures recommenced. For participants who miss or vomit pravastatin dose on Day 2, that visit should be rescheduled within 2 days if possible, holding the first dose of TB medications until after these Day 2 PK draws. For participants who miss doses on one of the two days preceding the PK collection on Day 15 (steady state) or who vomit that day's doses, the Day 15 visit should be rescheduled for  $\geq 2$  days later.

Specimens will be obtained, processed, and assayed according to the PK standard operating procedures manual.

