## ***Data Analysis***

The current study is a 2-week, 4-arm dose-escalation trial to determine the safety/tolerability and PK of pravastatin when co-administered with the standard drug regimen for drug-susceptible TB (Rifafour). Participants will receive standard anti-TB therapy and pravastatin beginning at a dose of 40 mg once daily. Each subsequent arm (pravastatin 80 mg, 120 mg, and 160 mg) of this study will continue to recruit participants until at least 10 participants in each group are evaluable for full PK analysis.

The primary endpoints in this study are safety/tolerability and pravastatin exposures. A regimen will be deemed safe and well tolerated if none of the participants require treatment discontinuation for a pravastatin-related adverse reaction and  $\leq 3$  participants experience a pravastatin-related grade 3 (or higher) adverse event during the 14-day study period and follow up. PK parameters (e.g., area under the concentration-time curve over 24 hours ( $AUC_{0-24}$ ), minimum concentration ( $C_{min}$ ), maximum concentration ( $C_{max}$ ), and oral clearance (Cl/F)), will be estimated for pravastatin from intensive sampling data after a single dose of pravastatin (baseline PK, prior to initiation of TB treatment) and after 14 days of co-administration with the first-line anti-TB regimen. Based on PK data of pravastatin when co-administered with rifampin ( $T_{max} = 1$  hour,  $T_{1/2} = 1.5$  hours), plasma samples will be collected for pravastatin measurements by LC-MS/MS at the following time points: pre-dose, 0.5 hrs, 1 hr, 1.5 hrs, 2 hrs, 3 hrs, 4 hrs, 6 hrs, and 8 hrs. Pravastatin exposures will be calculated using a noncompartmental approach using standard PK software, e.g., Phoenix WinNonLin. Using all PK data, a PK/PD model will be developed to evaluate the relationship between drug exposures (e.g.,  $C_{max}$ ,  $T_{max}$  or  $AUC_{0-24}$ ) and outcomes (e.g., safety/tolerability).  $C_{max}$  and  $t_{max}$  will be taken directly from the original data. The terminal log-linear phase of the plasma concentration-time curve will be identified visually for each curve.

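### Under the Data Analysis criterion, the no-discontinuation clause makes the verdict for one to three affected participants depend on whether toxicity is found before or after pravastatin ends

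*Combined protocol and SAP*

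**What the plan says.** **The verdict.** Section 18, Data Analysis, has two conditions that must both hold. The discontinuation clause allows no one: "A regimen will be deemed safe and well tolerated if none of the participants require treatment discontinuation for a pravastatin-related adverse reaction". The count clause allows up to three participants, over a stated window: "participants experience a pravastatin-related grade 3 (or higher) adverse event during the 14-day study period and follow up".

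**The stopping criteria.** Section 5 requires permanent discontinuation for Grade 3 or higher CK ("participants will permanently discontinue statin but will be requested to attend follow-up visits until study end"). For the liver, it says "Study treatment will be permanently discontinued if any of the following criteria are met" and lists ALT above 5 x ULN without symptoms, ALT above 3 x ULN with symptoms of hepatitis, and ALT above 3 x ULN with bilirubin at least 2 x ULN.

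**Dosing.** The Abstract gives pravastatin alone on Day 1, and then "pravastatin + Rifafour will be given on Days 2-15". Section 4 confirms a dose at the final PK visit: "steady-state PK assessment at Day 15 immediately prior to administration of study medications".

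**Testing.** Section 4 and Appendix 1 schedule liver tests and "CK, serum creatinine" on Days 7, 15, 21 and 30. Safety Evaluation lists Days 7, 15 and 30 only.

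**The escalation rules.** Two other parts of section 18 govern escalation. The decision table fails Arm 1 at one participant, and Arms 2 to 4 at three, with an attributed Grade 3 or higher musculoskeletal, CK or liver event. The rule for initiating new dosing cohorts acts at any three participants. Neither has a discontinuation term or refers to the study day.

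**The concern.** A zero-tolerance clause that turns on stopping a drug works only while there is drug left to stop. After the last dose, a participant can meet a permanent-stop criterion without any discontinuation following. Read literally, the Data Analysis criterion then gives different verdicts for the same toxicity, depending on when the blood was drawn.

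The toxicity most likely to be missed is a laboratory change without symptoms that develops late in the two weeks of dosing. A dose could be called safe and well tolerated although up to three participants met the protocol's own criteria for permanent discontinuation. That verdict is one of the primary endpoints named in Data Analysis.

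**Working it through.** The plan gives no operating characteristics for its safety rule, so there is no figure to reproduce.

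**Step 1: schedule**

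| Scheduled CK and liver test | Position relative to last dose (Day 15) | Can it lead to stopping pravastatin? |
|---|---|---|
| Day 7 | Days 8 to 15 remain (8 doses) | Yes |
| Day 15 | Day of last dose | Only if the result is back before the dose; no turnaround time is given |
| Day 21 | 6 days after | No |
| Day 30 | 15 days after | No |

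One of the four tests clearly falls while doses remain. On the Safety Evaluation list it is one of three.

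**Step 2: identical event, different day (Data Analysis rule)**

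- CK of 15 x ULN attributed to pravastatin is Grade 3. One case on Day 7 fails the dose. One, two or three cases first found after dosing do not. Four fail it on any day.
- ALT of 4 x ULN with bilirubin of 2.2 x ULN meets a stopping criterion. Both values are Grade 2 in the section 5 table (ALT 2.5 to below 5; bilirubin 1.6 to below 2.6). On Day 7 it fails the dose. On Day 21, by laboratory grade alone, it enters neither clause. ALT between 3 and 5 x ULN with symptoms behaves the same way unless a symptom is itself Grade 3 or higher.

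**Step 3: size**

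Let n be the arm size (5 in Arm 1, 10 in the others), p the proportion with a pravastatin-related stop-level event by Day 30, and f the share of those events found on Day 7. The values of p and f are assumptions. Every event is taken to be Grade 3 or higher, and n is held fixed although participants who stop are replaced.

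P(pass) = sum over k = 0 to 3 of C(n,k) p^k (1-p)^(n-k) (1-f)^k

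If every stop-level event counted with zero tolerance, P(pass) = (1-p)^n, which is the case f = 1.

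Probability that a dose passes, n = 10:

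| Rule | p = 5% | p = 10% | p = 20% |
|---|---|---|---|
| Data Analysis, all found on Day 7 (f = 1) | 59.9% | 34.9% | 10.7% |
| Data Analysis, f = 50% | 78% | 60% | 34% |
| Data Analysis, f = 25% | 88% | 77% | 56% |
| Data Analysis, all found later (f = 0) | 99.9% | 98.7% | 87.9% |
| Decision table, any day (fails at 3 or more) | 99% | 93% | 68% |

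In Arm 1 (n = 5, p = 10%), the Data Analysis rule fails the dose 41.0% of the time if all events are found on Day 7 and 0.05% if all are found later. The decision table gives 41.0% on any day.

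**Step 4: a low event rate**

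The Tolerability section reports CK above 10 x ULN in 4 of 464 patients on 80 mg, or 0.86%. With n = 10 and f = 25%, P(pass) is 97.9% as written and 91.7% if every stop-level event counted. For all three 10-person arms to pass, taken as independent with the same rate, the figures are 0.979^3 = 94% and 0.917^3 = 77%.

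**The case against.** **Escalation.** A reader might infer that the trial's escalation decisions depend on the day a toxicity is found. The documents do not support that. Under the decision table, one attributed Grade 3 CK event fails Arm 1 on any day, and in Arms 2 to 4 one such event fails the dose on no day, including Day 7. The cohort-initiation rule also counts the Grade 2 liver patterns of Step 2, though only at three participants. The day dependence belongs to Data Analysis alone.

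**Late events.** A reader might also infer that late toxicity escapes altogether. It does not: the count clause covers follow-up, a fourth Grade 3 or higher case fails the dose whenever it is found, and the DSMB reviews each cohort before escalation. Daily adverse event assessment, CK testing prompted by Grade 3 myalgia, and unscheduled visits can all lead to stopping between scheduled tests. What can slip past the discontinuation clause is mainly laboratory change without symptoms first found on Day 15 or later.

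**Wording.** To require discontinuation could mean meeting a criterion rather than actually stopping, and the follow-up window could be read as covering both clauses. On that reading the problem disappears, but the text does not settle it. Nor does it say whether treatment here means pravastatin alone; Rifafour continues after Day 15.

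**Inputs.** No document supports particular values of p or f, and the 0.86% rate comes from a mean exposure of 8.6 months and covers CK only. The direction of the effect follows from the rule; its size is illustrative.

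**Zero tolerance to Day 30.** Since Grade 3 CK is itself a stopping criterion, and ALT above 5 x ULN is essentially Grade 3, this would leave the allowance of three almost empty for these events. It would also widen the conflict with the decision table, which tolerates two in Arms 2 to 4. This objection stands and shapes the fix.

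**Conclusion.** The point holds for the Data Analysis criterion, and for one to three affected participants. Among scheduled tests, only Day 7 clearly can trigger the discontinuation clause. At p = 10% in a 10-person arm, the probability of failing the dose runs from 65.1% with all events found on Day 7 to 1.3% with all found later.

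This rests on four things: a literal reading of the clause as actual stopping of pravastatin; a Day 15 result that arrives after that day's dose; detection by scheduled tests rather than by symptoms; and the assumed p and f. The calculation does not cover stop-level events that are only Grade 2 by laboratory value. For those the gap is wider, because a late finding may count nowhere.

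**What to change.** 1. Reword the discontinuation clause in Data Analysis so that it counts participants with a pravastatin-related event that meets a permanent-discontinuation criterion of section 5 at any time from first dose to Day 30, whether or not dosing had ended. The stopping criteria themselves stay as they are.
2. Reconcile the number of such participants tolerated across Data Analysis, the decision table and the cohort-initiation rule, so that one day-independent rule gives both the safety verdict and the escalation decision. The number should come from that reconciliation; rewording the clause alone does not settle it.

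**Cost.** The text of these three rules changes, with no new visits or tests. If zero tolerance is kept, a safe dose passes somewhat less often: about 98% falls to 92% per 10-person arm, and 94% to 77% for all three, at the 0.86% rate with f = 25%. Events found after Day 15 need careful attribution, because Rifafour continues.
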